After screening, subjects will receive the following tests: (1) Measurement of hepatic glucose production, substrate oxidation and plasma ketone/lactate/insulin/glucagon concentrations; (2) (Measurement of whole body norepinephrine turnover with ^3H -norepinephrine infusion; (3) Measurement of heart rate variability; (4) Measurement of liver fat content with ^1H -MRS; (5) 75-grams oral glucose tolerance test (OGTT)

The studies will be performed in a random order.

After the completion of the above studies, subjects in each group will be randomized (in 2:1 ratio) to receive for 12 weeks, empagliflozin 25 mg per day (n=24) or placebo (n=12), in a double blind fashion. The drug treatment will be started (day 1) on the day of the second hepatic glucose measurement (see specific details below). On day 2, the measurement of heart rate variability and norepinephrine turnover will be repeated. Subjects will continue treatment with the drug (empagliflozin or placebo) that they received during the second hepatic glucose measurement for 12 weeks and at the end of 12 weeks, all baseline tests will be repeated.

The treatment period could be extended based upon the circumstances until the repeat studies are completed.

Tests	Baseline	Day 1-3	12 Weeks
OGTT	OGTT		OGTT
HGP	Short	Long	Short
NE	NE	NE	NE
MRI	MRI		MRI
DEXA	DEXA		
HRV	HRV	HRV	HRV

The metabolic effects of empagliflozin lasted for 2 weeks in our previous studies (7). However, Ferrannini and colleagues (40) reported that at 4 weeks, the glucose effects of empagliflozin (HGP) are attenuated while the fat effects (fat oxidation and ketone production) are enhanced. Therefore, to evaluate the long term metabolic impact of SGLT2 inhibition, we decided to extend the treatment period in the current study to 12 weeks.

Specific Methods:

Screening: Medical history and physical examination will be performed. Blood samples will be drawn for CBC, blood chemistries, lipid profile, thyroid function and HbA1c. EKG will be performed.

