During the Oral-IV double tracer infusion study, only the ^{14}C -glucose which escapes the liver and non-hepatic splanchnic tissues appears in the systemic circulation, while all of the infused ^3H -glucose appears in the systemic circulation. Therefore, the difference between R_a calculated with ^3H -glucose and R_a calculated with ^{14}C -glucose represents the basal rate of hepatic plus non-hepatic splanchnic tissue glucose uptake. Thus, the basal rate of EGP will be calculated for ^3H -glucose as the ^3H -glucose infusion (dpm/min) divided by the steady-state plasma ^3H -glucose specific activity (dpm/mg). The rate of ^{14}C -glucose appearance will be calculated as the ^{14}C -glucose infusion rate (dpm/min) divided by the steady-state plasma ^{14}C -glucose specific activity (dpm/mg). The hepatic and non-hepatic splanchnic glucose uptake equals $R_{a3\text{H}-\text{glucose}}$ minus $R_{a^{14}\text{C}-\text{glucose}}$. Norepinephrine clearance rate will be calculated as ^3H -NE infusion rate (dpm/min) divided by the steady state plasma ^3H -NE radioactivity (dpm/ml) (between 12 and 20 min). Norepinephrine spill over (release) rate (pg/min), which reflects the sympathetic nervous system activity (53), will be calculated as the product of plasma norepinephrine concentration (pg/ml) and norepinephrine clearance rate (ml/min). The difference between norepinephrine spill over in empagliflozin-treated and placebo-treated subjects, in each group (i.e. NGT, IFG and T2DM), represents the effect of glucosuria on the sympathetic nervous system activity. The ratio between plasma ^3H -DHPG to ^3H -NE (between 20 to 120 minutes) will be used as an index of neuronal uptake of norepinephrine (54).

Values will be presented as mean \pm SD. Difference between means will be compared by ANOVA. Post hoc testing will be performed with the Bonferroni test.

The increase in HGP caused by glucosuria in each treatment group will be related to the change in norepinephrine spill over rate with Pearson's correlation in each treatment group. We anticipate a strong correlation between the two variables.

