Consistent with previous studies (57), we anticipate that IFG subjects will manifest increased hepatic fat content and reduced HGU. Further, we anticipate that SGLT2 inhibitors will cause a significant decrease in hepatic fat content, increase in basal HGU and reduction in FPG concentration back/close to the normal level. Because MRI spectroscopy quantitates hepatic triglyceride content, while toxic fat metabolites (e.g. fatty acyl Co-A, DAG and ceramide), are responsible for the inhibition of HGU, it is possible to observe an improvement in HGU and decrease in the FPG concentration in IFG and T2DM patients on day 3 without a significant reduction in hepatic fat content measured with MRI. Nonetheless, in such a scenario, the reduction in hepatic fat content should be detected after 12 weeks of treatment.

Lastly, we anticipate that, in addition to the increase in HGP, shift in fuel consumption, and change in autonomic nervous system activity, SGLT2 inhibitors will produce a significant decrease in FPG concentration in T2DM patients and the decrease in the FPG concentration will be accompanied with a small decrease in the fasting plasma insulin concentration and large increase in plasma glucagon concentration in association with an increase in plasma ketone concentration in T2DM subjects following empagliflozin administration. These results will provide strong evidence in support of an important role of the changes in plasma insulin and glucagon concentrations in the increase in plasma ketone concentration following SGLT2i administration. It follows, therefore, that combination therapy with antidiabetic agents which inhibit glucagon secretion and increase insulin secretion, e.g. GLP-1 RA, plus SGLT2i will decrease the risk of ketoacidosis associated with SGLT2i therapy in T2DM patients (14,15).

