We anticipate that empagliflozin will increase norepinephrine spill over to the plasma in T2DM patients as well, and that the increase in norepinephrine spillover will strongly correlate with the increase in HGP. Because the methodology utilized in the present study measures the rate of total body norepinephrine spill over, it is possible that the increase in epinephrine spill over from specific organs, e.g. kidney and splanchnic (primarily hepatic) tissue, will be diluted in the systemic circulation. Thus, it is possible that only a modest effect of empagliflozin on sympathetic activity will be detected. In such a scenario, measurement of organ specific (58), e.g. renal norepinephrine spill over (with renal vein catheterization) and splanchnic (with intraduodenal ³H-NE infusion and arterial or hepatic vein sampling) can be employed to quantitate the change in sympathetic activity in the kidney and liver.

Sample Size Calculation We powered the study to detect a significant increase in the basal rate of HGP following empagliflozin administration versus placebo. In previous studies, the increase in the rate of HGP versus placebo following empagliflozin administration was 0.34 ± 0.26 mg/kg.min. Therefore, we computed that 30 subjects in 2:1 randomization (20 empagliflozin and n=10 placebo) provide >90% power to detect a significant difference in HGP between empagliflozin-treated and placebo-treated subjects (in 3 groups comparison) at alpha <0.05. Therefore, to ensure 30 completers, we have set the sample size at 36 in each group.

Item 7 Risks Section:

Complete the following table to describe the risks of all **research procedures** listed in Step 2, Institutional Form (items 28-34). *Do not list risks of Routine care procedures here.*

X N/A, Risks are described in the informed consent document – do not complete this table.

Research procedures	Risks
example: 
• History and physical• Questionnaire• Laboratory tests	List the reasonably expected risks under the following categories as appropriate:
Add or delete rows as needed	
	

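### Cross-group mechanistic conclusions rest on within-group results; no arm-by-group contrast or pooled norepinephrine effect is prespecified

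*Combined protocol and SAP*

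**What the plan says.** **Effects defined.** In Item 6, Data Analysis Plan, the effect on sympathetic activity is a within-group arm difference: "The difference between norepinephrine spill over in empagliflozin-treated and placebo-treated subjects, in each group (i.e. NGT, IFG and T2DM), represents the effect of glucosuria". The HGP effect is defined in the same way, group by group.

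**Test named.** Means are to be compared by ANOVA with Bonferroni post hoc testing. The factors are not stated. No arm-by-group term, between-group contrast of arm effects or pooled arm effect is mentioned. The one difference of differences in the document is in Sub-Study 2, and it concerns fluid replacement.

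**Conclusions foreseen.** Under Anticipated Results and Potential Problems, the plan expects no significant ketone rise and no significant change in the glucagon-to-insulin ratio in NGT and IFG. It would take this as strong evidence against a role for that ratio in the HGP rise. For T2DM it expects falls in insulin and rises in glucagon and ketones, and says of the ketone rise: "These results will provide strong evidence in support of an important role of the changes in plasma insulin and glucagon concentrations". Steps 6 and 7 of the working hypothesis in Item 3 make the same contrast: ketones are driven up in T2DM and stay unchanged in NGT.

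**Norepinephrine.** A rise is anticipated in all three groups. As a possible problem, because whole-body spillover may dilute organ-specific changes, the plan adds that "it is possible that only a modest effect of empagliflozin on sympathetic activity will be detected".

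**Sample size.** Only HGP is powered, on the statement that "30 subjects in 2:1 randomization (20 empagliflozin and n=10 placebo) provide >90% power". The target is the arm difference in HGP at an alpha below 0.05, described as a comparison involving three groups.

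**The concern.** A significant result in one group and a non-significant result in another do not show that the two effects differ. Small groups with the same true effect will often fall on opposite sides of the 5% line. A non-significant result in a small group also does not show that the effect is absent.

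Both inferences matter here. The argument that ketone production depends on insulin and glucagon draws its force from T2DM behaving differently from NGT and IFG. The argument that the HGP rise does not depend on the glucagon-to-insulin ratio needs that ratio to be truly unchanged in NGT and IFG. The plan goes on to infer that certain drug combinations would lower ketoacidosis risk, so a false group-specific mechanism would carry weight.

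For norepinephrine, a rise is expected in every group. A common effect is therefore a natural quantity to report, and it would use all the randomised subjects.

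**Working it through.** **Inputs from the documents**
- Allocation within each group: "subjects in each group will be randomized (in 2:1 ratio) to receive for 12 weeks".
- Completers: 20 empagliflozin and 10 placebo per group; "to ensure 30 completers, we have set the sample size at 36 in each group".
- Planning effect: "the increase in the rate of HGP versus placebo following empagliflozin administration was 0.34 ± 0.26 mg/kg.min". Reading the ± as an SD, which the text does not label, the standardised effect is 0.34/0.26 = 1.31 SD.
- Alpha 0.05, taken as two-sided because the sidedness is not stated.

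**Assumptions**
- Three groups of 30 completers with a common SD.
- No SD is given for the arm difference in ketones or norepinephrine, so results are shown for 0.8, 1.0 and 1.31 SD.

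**1. The plan's own power figure.** SE = 0.26 × √(1/20 + 1/10) = 0.101 mg/kg.min. Power for 0.34 is 92.2% (normal approximation) or 90.3% (noncentral t, 28 df). The stated figure reproduces as an unadjusted comparison within one group. At two-sided 0.05/3 it would be 83.7% or 79.0%.

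**2. Precision, in SD units**
- One group: SE = √(1/20 + 1/10) = 0.387. The 95% half-width is 2.048 × 0.387 = 0.79.
- Difference between two groups' arm effects: SE = √2 × 0.387 = 0.548. The half-width is 1.989 × 0.548 = 1.09 (84 df).
- Pooled over three groups: SE = 0.387/√3 = 0.224.

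An estimated effect of exactly zero in NGT would still be compatible with a true effect of up to 0.79 SD.

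**3. Comparing significance when the true effect is identical in all groups.** Let p be the power in one group (noncentral t, 28 df), with independent tests. Two given groups disagree with probability 2p(1−p). T2DM is significant and both others are not with probability p(1−p)².

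| True effect | p | Two groups disagree | T2DM only |
|---|---|---|---|
| 0.8 SD (assumed) | 0.514 | 50% | 12% |
| 1.0 SD (assumed) | 0.703 | 42% | 6% |
| 1.31 SD (HGP planning value) | 0.903 | 18% | 0.9% |

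**4. Power of the direct contrast.** Suppose one group has the full 0.34 and another has none. The SE of the difference is √2 × 0.101 = 0.142, which gives 66% power (84 df). For T2DM against the mean of NGT and IFG it is 78%. If the difference is half as large (0.17), these fall to 22% and 28%.

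**5. Pooled norepinephrine effect.** The effect detectable with 80% power is 1.12 SD in one group and 0.63 SD pooled. At 0.8 SD, power is 51% in one group and 94% pooled.

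**The case against.** **The ANOVA may already cover this.** With two arms and three groups, a crossed ANOVA would yield both an interaction test and an overall arm effect. A reader might infer that the trial has no such test and will never estimate a pooled effect. The text does not support that, because it is silent on factors. What stands is that neither is prespecified.

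**A modest norepinephrine effect is not the expectation.** A reader might infer that it is. The plan anticipates a rise that correlates strongly with HGP; the modest effect is a contingency, with organ-specific measurement as the fallback. This objection stands.

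**These are anticipated results, not decision rules.** The T2DM conclusion follows the T2DM results alone, and the NGT/IFG conclusion is a dissociation within those groups, so the cross-group ketone contrast is partly implicit. This is fair. But the same section says what the results will be taken to prove, and the Item 3 hypothesis states the contrast. The objection also shows that an interaction test would not repair the NGT/IFG inference. That needs the confidence interval for the effect in those groups.

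**Pooling answers a different question.** Item 3 explains why NGT is informative by itself: glucose, insulin and glucagon are expected not to move there, so a sympathetic effect can be isolated. A pooled effect mixes NGT with T2DM, where those signals also act. This stands against replacing the group-specific estimates, but not against adding a pooled one.

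**The size depends on an assumed effect.** It does. At the HGP planning value, a spurious T2DM-only pattern is rare (0.9%), although pairwise disagreement is still 18%.

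**Conclusion.** The point holds as a gap in prespecification. The plan fixes within-group effects and an ANOVA without stated factors, yet foresees conclusions that need either a contrast between groups or evidence of no effect within NGT and IFG. Half-widths of 0.79 SD (one group) and 1.09 SD (difference between two groups) show that neither can rest on significance alone. How often comparing significance would mislead ranges from 18% to 50% for two given groups, depending on the true effect. Only the 1.31 SD end has a source in the documents, and that source concerns HGP, not ketones or norepinephrine.

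The sample size for HGP within one group is not in dispute; it reproduces.

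All figures rest on three groups of 30 completers. Item 5 counts two target populations, and the abstract speaks of diabetic and non-diabetic subjects. If NGT and IFG share one cohort of 36, precision in each is worse than shown. With only two groups of 30, pooled power at 0.8 SD is 82%, not 94%.

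**What to change.** For each outcome, prespecify one linear model with arm, glycaemic group and arm-by-group, and state the groups and their sizes. Then:

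1. Report each group's arm effect with its 95% CI from that model. Do not read non-significance in NGT or IFG as no effect; say which effect sizes the interval excludes.
2. Base any statement that something happens in T2DM but not in NGT or IFG on the arm-by-group contrast with its 95% CI. Since that contrast has only 66% to 78% power even for an all-or-nothing difference of the planned HGP size, do not read a non-significant contrast as equality.
3. Report the pooled norepinephrine arm effect alongside the group-specific effects, not in their place.

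The cost is analysis wording only, with no added subjects or procedures. There are two small downsides. The model assumes a common residual variance unless group-specific variances are allowed. The pooled effect also averages over groups in which glucose and hormone changes differ, so it should be described as an overall effect and not as the isolated neural one.

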Surprisingly, however, empagliflozin did not affect the fasting plasma insulin and glucagon concentrations in NGT subjects and caused only a modest reduction in fasting plasma insulin concentration (Figure 12) with a small, transient, non-significant increase in fasting plasma glucagon in IFG subjects (Figure 13). Consistent with our previous study (13), empagliflozin caused a significant increase in plasma ketone concentration in T2DM patients (from 0.52 ± 0.04 to 0.68 ± 0.3 , $p=0.03$), while plasma ketone concentration was not affected by empagliflozin treatment in either IFG (0.43 ± 0.03 vs 0.43 ± 0.03) or NGT (0.53 ± 0.04 vs 0.45 ± 0.07) subjects following empagliflozin treatment (Figure 14). The lack of increase in plasma ketone concentration in NGT subjects is surprising in light of the large shift in fuel consumption during the fasting state caused by empagliflozin in non-diabetic subjects (decrease in RQ from 0.81 to 0.74). Collectively, these results demonstrate that: (1) Although SGLT2 has been shown to be present in the alpha cell and SGLT2i have been shown to directly stimulate glucagon secretion from the alpha cell (41), it is likely that, in man *in vivo*, the decrease in plasma glucose concentration in T2DM subjects following SGLT2 inhibition is the principal signal causing the decrease in plasma insulin concentration and increase in plasma glucagon concentration, (2) mechanism(s) other than the increase in plasma glucagon and decrease in plasma insulin concentration (likely neuronal) stimulates HGP and cause a shift in substrate oxidation following SGLT2 inhibition in NGT subjects and IFG subjects, and (3) the increase in plasma glucagon concentration and/or decrease in plasma insulin concentration is an important signal for the increase in ketone production following SGLT2 inhibition.

[figure not shown]

Figure 13: Fasting plasma glucagon concentration before (BL) and at day 1 to day 14 during empagliflozin treatment (25 mg/day) in IFG and NGT

[figure not shown]

Figure 14: Effect of empagliflozin treatment (25 mg/day) on plasma ketone concentration in NGT, IFG and T2DM subjects

[figure not shown]
[figure not shown]

Figure 15: Effect of dapagliflozin 3 μ M on pyruvate oxidation in hepatocytes in culture

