Our recent findings about the effect of empagliflozin on glucose metabolism in NGT and IFG subjects (Figures 10-14) and the effect of SGLT2 inhibitors on pyruvate oxidation in hepatocytes *in vitro* (Figure 15) require an update of our previous scheme (13) (Figure 6) describing the mechanism(s) responsible for the metabolic actions of SGLT2 inhibitors in T2DM patients. We suggest the following working hypothesis (Figure 16) which we will be testing in the current grant request: (1) Because empagliflozin did not stimulate glucagon secretion or inhibit insulin secretion in NGT subjects, it is likely that glucosuria stimulates HGP, at least initially, via mechanisms other than the increase in plasma glucagon concentration and decrease in plasma insulin concentration. Of note, the increase in HGP begins rapidly following dapagliflozin administration and before there is a significant increase in plasma glucagon concentration (Figure 2). This suggests a neurogenic origin, which results from activation of the renal nerves which communicate directly with the liver via neural connections in the portal circulation or indirectly via connections to the CNS. Consistent with this hypothesis, a recent study has demonstrated that the increase in HGP in dogs following hypoglycemia is markedly influenced by the brain (43). Further, renal denervation in experimental animals caused a significant increase in hepatic norepinephrine content (44). In the present grant proposal, we will measure the effect of empagliflozin on sympathetic activity with ³H-NE infusion; (2) In addition to inhibition of renal glucose absorption, SGLT2 inhibitors likely exert a direct inhibitory action on mitochondrial metabolism (possibly by inhibiting complex I[42]) causing inhibition of pyruvate oxidation and reduction in glucose oxidation. (3) The inhibition of glucose oxidation results in a reciprocal increase in fat oxidation and acetyl Co-A levels (4) The increase in fat oxidation aims to provide an alternative energy source to meet the metabolic demands of the cell. Because fat oxidation is associated with generation of FADH which can generate ATP via donating electrons to complex 2, thereby, bypassing the block at complex 1. (5) the decrease in the fasting plasma glucose concentration in T2DM patients following glucosuria stimulates glucagon secretion and inhibits insulin secretion resulting in an increase in plasma glucagon to insulin ratio; (6) the increase in glucagon to insulin ratio further stimulates and maintains the increase in HGP and stimulates the conversion of acetyl Co-A to ketones (possibly by stimulating the expression of hydroxyl methylglutaryl Co-A synthase [HMGS], the rate limiting step for the conversion of acetyl Co-A to beta hydroxybuterate [45,46]); (7) in subjects with NGT, SGLT2 inhibition does not affect the FPG concentration. Thus, plasma glucagon and insulin concentrations are not affected by SGLT2 inhibition, and the plasma ketone concentration does not increase (Figure 14). In the present grant request, we will test these hypotheses by: (1) examining the effect of empagliflozin on HGP, substrate oxidation, plasma ketone/lactate/insulin/glucagon concentrations, hepatic fat content, basal hepatic glucose uptake and sympathetic nervous system activity in NGT, IFG and T2DM patients with FPG concentration <160 mg/dl using state-of-the-art techniques. Because empagliflozin does not affect the FPG, insulin and glucagon concentrations in NGT subjects, this allows us to provide definitive evidence for the role of sympathetic activation in the increase in HGP caused by empagliflozin, and (2) examination of the effect of empagliflozin on substrate oxidation, hepatic fat content, FPG concentration, and hepatic glucose uptake during the fasting state in IFG

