Anticipated Results and Potential Problems: Based upon our preliminary results, we anticipate that empagliflozin will produce a large increase in HGP in NGT subjects which will maintain the FPG concentration at the fasting level. Further, because the FPG concentration does not change following empagliflozin administration, we anticipate that neither the fasting plasma insulin nor glucagon concentrations will be affected by empagliflozin. Likewise, we anticipate a large increase in HGP in IFG subjects with no significant change in the fasting glucagon to insulin ratio. We also anticipate a shift in substrate oxidation (i.e. decrease in glucose oxidation and increase in fat oxidation) in NGT and IFG subjects with no significant increase in plasma ketone concentration. These results will provide strong evidence against a significant role of the increase in plasma glucagon to insulin ratio in the increase in HGP and shift in fuel consumption from glucose to fat oxidation following SGLT2 administration. Further, we anticipate that SGLT2 inhibitors will alter autonomic balance and increase sympathetic nervous system activity in NGT and IFG subjects and that the increase in sympathetic nervous system activity will be, at least in part, responsible for the increase in HGP. Thus, we anticipate a strong correlation between the increase in sympathetic nervous system activity and the magnitude of increase in HGP in IFG and NGT subjects.

It will be of great interest to examine the effect of empagliflozin on plasma lactate concentration in NGT subjects. If, as anticipated, empagliflozin causes a robust increase in fat oxidation, decrease in glucose oxidation and increase in lactate concentration in NGT subjects, without a change in ketones, FPG, FFA, insulin, and glucagon concentrations, this will provide a strong evidence in support of a direct effect of the drug on mitochondrial substrate oxidation, independent of SGLT2 inhibition. In such a scenario, future studies with MRI spectroscopy and ¹³C-acetate infusion to quantitate hepatic TCA cycle activity (55,56) before and immediately after the administration of SGLT2 inhibitor in NGT subjects will provide direct evidence in support of an inhibitory effect of SGLT2 inhibitor on mitochondrial function independent of SGLT2 inhibition.

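### Unaffected hormones in NGT and a non-significant glucagon-to-insulin change in IFG are to be read as strong evidence against a significant hormonal role, but no margin is set and 20 versus 10 completers may not exclude a moderate change

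*Combined protocol and SAP*

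**What the plan says.** Under Anticipated Results and Potential Problems (Item 6), the plan forecasts for NGT subjects that "neither the fasting plasma insulin nor glucagon concentrations will be affected by empagliflozin", with no criterion for what counts as unaffected. For IFG subjects it forecasts a large HGP increase "with no significant change in the fasting glucagon to insulin ratio". From this pattern, together with a shift in fuel use without a rise in ketones, it concludes: "These results will provide strong evidence against a significant role of the increase in plasma glucagon to insulin ratio in the increase in HGP". The sentence goes on to cover the fuel shift as well.

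The Background (Item 3, working hypothesis) is firmer. Because empagliflozin is taken not to alter FPG, insulin or glucagon in NGT subjects, "this allows us to provide definitive evidence for the role of sympathetic activation in the increase in HGP caused by empagliflozin".

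The Data Analysis Plan in Item 6 compares means by ANOVA with Bonferroni post hoc tests. Nowhere is there a margin, an equivalence test, an interval rule or a power statement for insulin, glucagon or their ratio. The main Sample Size Calculation concerns HGP: "30 subjects in 2:1 randomization (20 empagliflozin and n=10 placebo") are said to "provide >90% power to detect a significant difference in HGP between empagliflozin-treated and placebo-treated subjects".

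The pilot data behind the forecast (Item 3) come from 8 NGT and 8 IFG subjects treated for two weeks, with no placebo arm described. In the IFG subjects insulin fell modestly and there was a "small, transient, non-significant increase in fasting plasma glucagon in IFG subjects".

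**The concern.** A difference test that fails to reject shows absence of a difference only if the interval around the estimate is narrow enough to rule out changes that matter. The plan does not say how narrow that must be, and the sample size was not chosen with these hormones in mind. On the hormone half of the argument, noise then works in favour of the hypothesis: a less precise assay or more dropout makes a non-significant ratio more likely, and the plan would read that as support for a non-hormonal signal.

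At stake is the mechanistic conclusion in NGT and IFG. A real but moderate hormonal contribution could be reported as strong evidence that the contribution is not significant. The pilot gives some reason for care: in IFG both hormone shifts were in the direction that raises the ratio, yet the Purpose section (Item 4) summarises the NGT and IFG findings as showing no significant change in it.

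**Working it through.** **Inputs from the documents.** Completers per group: 20 empagliflozin, 10 placebo. HGP effect and spread used for sizing: 0.34 ± 0.26 mg/kg·min (± read as SD). Alpha: 0.05 (two-sided assumed; the plan does not say). T2DM ratio change on empagliflozin: 5 to 11 (Item 3).

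**Inputs assumed.** The documents give no SD for the change in the log glucagon-to-insulin ratio in NGT or IFG. I use 0.3, 0.5 and 0.7 to show the range.

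**1. The plan's own figure.** SE factor = √(1/20 + 1/10) = 0.387. Standardised HGP effect = 0.34/0.26 = 1.31, so the noncentrality is 1.31/0.387 = 3.38. Power on 28 df, two-sided 0.05, is 90.3% (92.2% by the normal approximation). The stated power of over 90% for HGP reproduces.

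**2. Precision for any other endpoint at the same size.** 95% half-width = t(0.975, 28) × 0.387 × SD = 2.048 × 0.387 × SD = 0.79 SD. The difference detectable with 80% power is 1.12 SD. If the observed difference is zero or positive, a non-significant result has an upper limit between 0.79 SD and 2 × 0.79 = 1.59 SD. With all 36 subjects retained (24 versus 12) the half-width is 0.72 SD.

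**3. In fold-change terms.** The T2DM change is ln(11/5) = ln 2.2 = 0.788. Half of it is 0.394, a 1.48-fold rise. Miss probability = 1 − noncentral-t power, with noncentrality = log change / (0.387 × log-SD).

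| Assumed log-SD | Half-width as fold change | 1.48-fold rise missed | 2.2-fold rise missed |
|---|---|---|---|
| 0.3 | 1.27 | 9% | <0.1% |
| 0.5 | 1.49 | 50% | about 2.5% |
| 0.7 | 1.74 | 71% | 20% |

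These figures use an unadjusted 0.05. Bonferroni adjustment over three contrasts would widen the half-width to 0.99 SD.

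**4. Group definition.** Item 5 lists subjects with FPG below 126 mg/dl as one population, while the analysis text names NGT and IFG separately. If one group of 36 had to cover both, an assumed even split leaves about 10 versus 5 completers each and a half-width of 1.18 SD.

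**5. What an interval rule would deliver.** Take 0.394 (half the T2DM log change) as an illustrative upper margin and suppose there is no true change. The 95% upper limit falls below the margin in about 91% / 50% / 29% of trials at log-SD 0.3 / 0.5 / 0.7.

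**The case against.** Several points on the other side are sound.

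- **A large change would probably be seen.** A reader might infer that the design cannot exclude a large hormonal change. The figures do not support that: a T2DM-size doubling is detected with about 80% power or more at each assumed SD. The gap concerns moderate changes, and its width depends on an SD that the documents do not give.
- **This is a forecast, not an analysis rule.** The sentence stands under Anticipated Results, and the wording "no significant change in the fasting glucagon to insulin ratio" is used of IFG only; for NGT the text simply says the hormones will not be affected. Both are fair points. Still, this is where the plan says how these hormone results will be read, and nothing in the Data Analysis Plan replaces it.
- **The text does not say that hormones play no role.** A reader might take it that way, but it speaks of a significant role, credits sympathetic activity only in part, keeps the ratio as a sustaining stimulus to HGP in T2DM (Item 3), and gives hormones an important role in ketone production.
- **The neural hypothesis is also tested directly**, through norepinephrine spillover against placebo, heart rate variability, and the correlation of spillover with the HGP rise. A noisy glucagon assay cannot create those results, so the case does not rest on elimination alone. Equally, a positive spillover result does not exclude a parallel hormonal contribution.
- **Hormones are clamped experimentally.** The pancreatic clamp holds insulin and glucagon at basal levels, but it belongs to Sub-Study 1, which enrols T2DM patients only. It does not cover the NGT and IFG inference.

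**Conclusion.** The concern holds as a flaw of interpretation. The plan gives no criterion for unaffected hormones in NGT, uses non-significance in IFG, and calls the combined pattern strong evidence against a significant role of the ratio, with only a difference test planned and a sample sized for HGP. The half-width of 0.79 SD follows from the plan's own completer numbers. The miss rates of 9% to 71% for a 1.48-fold rise rest on assumed log-SDs of 0.3 to 0.7; at the low end the problem is small, at the high end serious. The stronger inferences, that a T2DM-size change would go unnoticed or that the neural conclusion depends wholly on a null hormone result, are not supported. The HGP comparison, its stated power and the randomisation are unaffected. This should be fixed, but it does not undermine the trial.

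**What to change.** In the Data Analysis Plan, for NGT and IFG separately, estimate the empagliflozin-minus-placebo difference in the change of the log glucagon-to-insulin ratio, and likewise of insulin and glucagon, each with a 95% confidence interval. State evidence against a significant role only if the upper limit for the ratio lies below a margin that the sponsor sets and justifies before unblinding. Half the T2DM log change is one illustration, not a recommendation. Otherwise report that a hormonal role is not excluded. Make the strong-evidence sentence in Anticipated Results conditional on that result, and soften the definitive-evidence claim in the Background.

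The cost is protocol wording and a few intervals from data already planned; no new visits or subjects are needed. The drawback is that the hormone question may end as inconclusive. Under the illustrative margin and no true change, that would happen in about 9% / 50% / 71% of trials at log-SD 0.3 / 0.5 / 0.7.
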